1.0 Objectives

1.1 Purpose:

We propose to develop an informatics system to assist people with memory impairment. Early stages of Alzheimer's and Alzheimer's related dementia often causes memory concerns. Persons with Memory Concern often cannot match names with faces or cannot recognize faces with a sure feeling of familiarity. Persons with Memory Concern (PWMC) may have difficulty remembering the names of family members and friends or may address them with a wrong name. They recognize the faces they see daily, such as a spouse or caregiver, but they may confuse visiting friends and grandchildren. The inability to remember names or relationships contributes to isolation and deeply affects their social lives. The proposed solution is a Smartwatch Reminder (SR) system to conspicuously provide this information to the PWMC when needed. This system will automatically transmit pictures and relevant information to a smartwatch worn by the PWMC when family or friends visit. The system will be evaluated on the target persons with memory concern population to measure engagement and improvements in social interactions and well-being.

Phase I Aims:

Aim 1: The phase I will develop a prototype SR system with limited features. It will work on one model of smartphone and smartwatch. The prototype system can be used to get feedback from potential users.

Aim 2: Examine the feasibility of the SR system for PWMC.

The result of Phase I will include user feedback that demonstrates the acceptability and perceived utility of the system.

Phase II Aims:

Aim 3: Phase II will develop smartphone and smartwatch apps designed to work with the popular products of 2022. The project will provide a smartwatch and tablet for dyads in the treatment group. Family, friends, etc. of the treatment group participants will be able to download a smartphone app from an online store. Instructional material will be created to show the suggested information that can be entered into the app.

Aim 4: Evaluate whether the Smartwatch Reminders exerts positive benefits for PWMCs' social engagement and well-being via an embedded experimental mixed methods design that combines the collection and analysis of qualitative data within a traditional randomized controlled trial (RCT) design.

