3.0 Study Endpoints/Events/Outcomes

3.1 Primary Endpoint/Event/Outcome:

Phase I: Twenty care partners will complete a system review checklist and context of care items in a dyadic interview setting. The intervention will be considered successful if at

SOCIAL PROTOCOL (HRP-580)

PROTOCOL TITLE: A Mobile Informatics Solution to Aid in Memory

VERSION DATE: 7/1/2022

least 75% of participants score an average of 4 (out of 5) points or higher on the checklist, indicating that SR met their needs (i.e., indicated agree or strongly agree that the SR was useful, acceptable, and feasible overall). This threshold has been used as a benchmark for success in prior research evaluating technological interventions for PWMC and their care partners(6-8). If the criteria for success are not met, the technology will be refined based on feedback and suggestions from PWMC and care partners, before conducting additional testing with the improved prototypes. Ample qualitative feedback will be available via the dyadic interviews to guide such refinement.

Phase II: Baseline and 6 month data will be used in a 2x2 repeated measures analysis of covariance to examine whether use of the SR results in statistically significant changes in PWMC negative health transitions and , social interaction, pleasant events, social stress, loneliness, relationship closeness, and community engagement and care partner well-being, such as social support, depression and burden (9). The primary independent variable in the proposed investigation consists of an indicator variable for random assignment into the SR treatment condition or the attention control group. Additional analyses will determine if covariates (context of care, mobile device proficiency, and dementia severity indicators) significantly vary across the SR treatment and attention control groups at baseline and over 6-months. If statistically significant variations between the SR treatment and control groups are found, baseline and/or change scores for these covariates will be included in all repeated measures analyses of covariance tests to provide additional statistical control.

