to the SR along with the training procedures or an attention control group. Randomization (participant is assigned to either the treatment or control condition) will be completed via an a priori list generated from <http://randomizer.org> by [name]. For those in the SR treatment group, the research coordinator will schedule a time to introduce the SR to the PWMC and the care partner via Zoom or telephone.

To ensure blinding is maintained, the RA will not have access to the password-protected database containing participants' group assignment, and will not review survey data completion (which would un-blind the RA since all of the treatment participant follow-up surveys will contain the system review and all control participant follow-up surveys will not). Additionally, opaque, sealed envelopes will be created for the research coordinator to reveal which group each participant was randomized into. The outside of each envelope will be labeled with a dyad's ID and the inside will contain their group assignment, which will ensure integrity of the randomization order since no one will be able to change the order once the envelopes are created.

5. **3-month survey or contact call:** A survey will be administered (either online in Qualtrics or via mail, if preferred) by the RA to all participating care partners and PWMC 3 months following enrollment. A brief disposition survey will be administered before the 3- and 6-month follow-up surveys to determine if the PWMC has moved or passed away. A system review of the SR will be assessed via a checklist and open-ended questions (see Appendix) and will be sent only to dyads in the intervention group in their follow-up survey (the RA will remain blinded because they will email participants personalized links to the survey which do not indicate whether the participant is receiving the SR system review or not in their follow-up survey). The attention control group will receive a 3-month contact call from the research coordinator. Based on our prior experience, PWMC and care partners in an attention control group will often seek information and psychosocial support during these calls. We will provide free information resources (e.g., brochures or websites of the Alzheimer's Association). See section 10.2 about re-assessing each PWMC's capacity to consent at each time point.

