The RA will complete disposition calls or emails ± 7 days prior to a scheduled follow-up survey. The RA will contact care partners within 1 week of a missed survey to resend, and update participants' contact information as needed throughout the project. RA will follow up with CG and PWMC via email reminders at 1, 2 and 3 weeks past the date a survey was sent if it is still incomplete. Additionally, at 3 weeks RA/RC will try to contact dyad via phone. If no response, participants will be considered lost to follow up (LTFU) for that time point.

Note: If LTFU occurs at baseline, the dyad will be withdrawn from study as they were not randomized.

An annual project newsletter will be sent to all participants to provide updates on study progress as well as provide seasonal caregiving tips. Finally, in order to provide additional rapport and incentive to participate in the attention control group, all PWMC and care partner dyads in the proposed project will be provided with up to a \$100 participation incentive following completion of their 6-month survey (see more information in Payment section 12.5). Those in the treatment group who are selected for and complete a semi-structured interview will receive an additional \$50 participation incentive.

Phase II Data Collection.

The RA will administer the baseline and follow-up surveys at 3- and 6-months, and will be blinded to randomization. Completion of these follow-ups may occur outside of the timeframe for initial contact based on participant scheduling needs.

Baseline, 3-Month and 6-Month Survey. The RA will administer all surveys (see Appendix). The surveys are designed to collect information from both PWMC and care partners. The selected measures have strong psychometric properties, sensitivity to change, and clinical relevance in the evaluation of health technology such as SR. Our past experience in distributing surveys of similar length indicate that they take PWMC and their care partners approximately 20-45 minutes to complete. Mean and sum scores will be calculated for all scales.

SOCIAL PROTOCOL (HRP-580)

PROTOCOL TITLE: A Mobile Informatics Solution to Aid in Memory

VERSION DATE: 7/1/2022

- Context of care (baseline only). Care partners will complete context of care variables include geographic location, time since diagnosis, type of dementia diagnosis, Medicaid status, living arrangement of the PWMC, and demographics of the PWMC and the care partner.

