- Dementia severity. Care partners will complete validated measures of dementia severity including the PWMC's dependence on assistance with 6 activity of daily living tasks and dependence on assistance with 6 instrumental activity of daily living tasks(16-18, 50-52). An 8-item scale will assess the intensity of PWMCs' memory losses, communication deficits, and recognition failures at each time point (memory impairment)(19, 20). From the Dementia Severity Rating Scale, we are using one item about the PWMC's recognition of others (53). Additionally, during screening, the PWMC will complete the Telephone Interview for Cognitive Status (TICS-40) developed from the Aging, Demographics, and Memory Study), which will assess their level of dementia severity at the beginning of the study (50).
- Social interaction. Questionnaires will be administered to care partners to determine the frequency and quality of PWMCs' interaction in six different areas: in-person visits; telephone/video calls; traditional mail correspondence, text messaging, or email; and social media. Per the recommendations of prior research on informal long-term care, a prior week estimate will be completed that includes frequency and duration of each activity(22). A 7-day time-window was chosen as it is less prone to recall error. In addition to frequency data, satisfaction with the quality of interaction will be assessed on a simple 5-point scale, similar to prior reliable measures utilized in Alzheimer's disease and related dementias care partner intervention studies(23).
- Pleasant Events/Social Engagement. Care partners will complete the Pleasant Events Schedule-AD (PES-AD) Short Version (24, 25) for PWMCs. The PES-AD Short Version includes 20 items of events and activities for PWMCs. As originally constructed, the items of the PES-AD were within the capacity of individuals suffering from the earlier/milder stages of dementia, and thus were appropriate for inclusion in this Phase II project(24, 25). Items are rated according to their frequency during the past month and how much the PWMC enjoys the activity. An overall summary score assessing frequency of engagement in enjoyable activities is generated by multiplying each frequency and enjoyment item with each other and summing the resulting responses. The PES-AD has demonstrated excellent reliability and validity(24, 25).

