- Global Health. The PWMCs' overall health and quality of life are being measured using the PROMIS Scale v1.2 – Global Health (26). This assesses various aspects of health and life, such as ratings of mood, satisfaction with social activities/relationships, average pain, etc. through a series of 10 questions asked of the PWMC.
- Mobile Device Proficiency and social media use. The Mobile Device Proficiency Questionnaire (MDPQ-16; short form) is a 16-item scale used to measure how proficient the CP and PWMC are using various new technologies, such as tablets and their different features (27). The CPs' social media usage is also being measured using 3 questions developed by the research team.

SOCIAL PROTOCOL (HRP-580)

PROTOCOL TITLE: A Mobile Informatics Solution to Aid in Memory

VERSION DATE: 7/1/2022

- Social Support/Loneliness. Socioemotional support will be measured on a five-item scale to assess the affective assistance provided to the care partners by relatives or friends at each time point(19, 20). The Lubben Social Network Scale-6 (LSNS-6) is a six-item scale that assesses social isolation among the CP and PWMC (55). Loneliness will be measured with the 3-item Short Scale for Measuring Loneliness in Large Surveys(28).
- Care partner well-being. The 11-item Eriksonian Psychosocial Stage Inventory - Identity scale(29) will be administered to assess changes in identity coherence. The 10-item Center for Epidemiological Studies-Depression scale will be used to measure care partner depressive symptoms(30, 31).
- Relationship closeness. A 6-item measure of Relationship Closeness (32) will be used to evaluate the quality of the relationship between the PWMC and their care partner. This 6-item measure is part of the Stress Process Model for Residential Care (SPM-RC), developed by Whitlatch and colleagues and based on the Stress Process Model (SPM) for dementia caregiving. The measure assesses caregiver agreement with statements about their relationship with their relative using a 4-point Likert scale (1=strongly disagree, 4=strongly agree). Higher scores indicate a closer relationship (range 6-24).

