audit trail). In addition, patterns that link particular themes will be identified and discussed in successive meetings between [name] and [name] to identify more complex processes of Smartwatch use or this technology's pathways to benefit PWMC and their care partners. During monthly team meetings, the development of codes, categories, and themes will be reviewed with the other academic investigators (Drs. [name] and [name]) and the AME team to yield any additional input into these project components. The multiple team meetings and discussions will allow for an exploration of alternative interpretations of the qualitative data and will also provide a check regarding the quality and richness of the data collected during the embedded mixed methods components.

Phase II Quantitative Analysis: Data available at baseline and 6 months will allow for a 2x2 repeated measures analysis of covariance to examine whether use of the SR results in statistically significant changes in PWMC negative health transitions and , social interaction, pleasant events, social stress, loneliness, , relationship closeness, and community engagement and care partner well-being, such as social support, depression and burden (9). The primary independent variable in the proposed investigation consists of an indicator variable for random assignment into the SR treatment condition or the attention control group. IBM SPSS Statistics 21(41) will be used to conduct these analyses, as it supports a range of univariate, bivariate, and multivariate statistical analysis procedures. The team has extensive experience conducting longitudinal analyses on their prior research on dementia(5, 6, 42-44). Our proposed analyses will provide in-depth tests of the study hypotheses. Outcomes will include statistical significance of within-subjects, or 6-month change, in those in the Smartwatch Reminder treatment or control groups on key outcome variables (see above). Additional analyses will determine if covariates (context of care, mobile device proficiency, and dementia severity indicators) significantly vary across the SR treatment and attention control groups at baseline and over 6-months. If statistically significant variations between the SR treatment and control groups are found, baseline and/or change scores for these covariates will be included in all repeated measures analyses of covariance tests to provide additional statistical control.

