Phase II: A repeated measures analysis of covariance (ANCOVA) will be utilized to capitalize on the randomized design and the two sets of data that will be collected. The number of PWMC-care partner dyads to be enrolled to address study hypotheses was determined using power analysis procedures(45, 46). A sample size of 100 to identify a medium statistical effect (standardized regression coefficient = 0.15) at a suitable level of statistical power (0.80 is considered an excellent power value) is able to effectively incorporate up to 6 baseline covariates that vary significantly across the randomly assigned Smartwatch Reminder treatment and control conditions if they exist (as random assignment is often used to ensure statistically comparable treatment and control conditions, we feel this is a conservative estimate of baseline covariates)(46). Specifically, we relied on statistical power tables by the expert statistician Cohen(46) to conduct our assessment of power. As noted in Table 2 of Cohen (1992)(45), an alpha level of .05, a medium effect size of .15 (as opposed to using specific measures, Cohen operationalized a medium effect size of .15 as one that is observable, and a survey across the social sciences suggested that this proposed effect size was close to the average of observed effects), and a multiple regression model (similar to an ANCOVA) that includes up to 6 covariates requires a sample size of 97. For these reasons, an expected sample size of 100 PWMC and care partner dyads will be sufficient to conduct the Phase II efficacy evaluation. We anticipate having less than a 3% attrition rate which will ensure we maintain sufficient power. As noted in various recommendations for mixed methods sampling, 20 participants is considered an adequate sample size for semi-structured interview protocols to ensure the richness and depth of open-ended data collected(36, 47).

17.3 Statistical Analysis:

Statistical analyses used will include calculation of frequencies, bivariate correlations, t-tests, chi-square tests, and repeated measures ANCOVA as detailed above.

17.3 Data Integrity:

SOCIAL PROTOCOL (HRP-580)

PROTOCOL TITLE: A Mobile Informatics Solution to Aid in Memory

VERSION DATE: 7/1/2022

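### The Phase II efficacy models may adjust for 6-month change in device proficiency and dementia severity, which the smartwatch may itself alter, so the treatment effect can be biased

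*Combined protocol and SAP*

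**What the plan says.** Section 17.1 (Phase II Quantitative Analysis) sets one efficacy model: a 2x2 repeated measures ANCOVA on baseline and 6-month data, with randomised arm as the main independent variable. Context of care, mobile device proficiency and dementia severity indicators are compared between arms, both at baseline and over the 6 months. Then: "If statistically significant variations between the SR treatment and control groups are found, baseline and/or change scores for these covariates will be included". Section 3.1 repeats the rule for the Phase II endpoint: "baseline and/or change scores for these covariates will be included in all repeated measures analyses of covariance tests". Neither section calls this exploratory, and neither keeps a model free of change scores.

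The sample size case in section 17.2 is narrower. It says 100 dyads can "effectively incorporate up to 6 baseline covariates that vary significantly across the randomly assigned Smartwatch Reminder treatment and control conditions". It does not mention change scores.

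On the covariates themselves:

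- **Dementia severity** (section 5.2) includes an 8-item scale of "memory losses, communication deficits, and recognition failures at each time point", plus a single item on recognising other people.
- **Device proficiency** (section 5.2) is "used to measure how proficient the CP and PWMC are using various new technologies, such as tablets".
- **What only the SR arm receives.** Section 1.1: "The project will provide a smartwatch and tablet for dyads in the treatment group". Section 5.2 (Randomization) contrasts full access "to the SR along with the training procedures or an attention control group".
- **Not at issue.** Context of care is collected at baseline only, and the TICS-40 is given at screening, so neither has a change score.

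**The concern.** Baseline covariates cannot be affected by the arm, so adjusting for them keeps the randomised comparison. Six-month change can be affected. If SR helps partly through a covariate, such as better recognition or more confident device use, holding that covariate's change fixed removes part of the benefit the trial is meant to detect. If SR moves the covariate but not the outcome, and both share a cause such as underlying decline, the adjustment creates an effect that does not exist.

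The significance trigger makes this worse. Apart from selective missing data or reporting, an arm difference in change after randomisation is either a treatment effect or chance. The more SR moves a covariate, the more often the rule adjusts for it. This applies to every outcome in the only Phase II efficacy model.

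**Working it through.** **The plan's own figure.** Section 17.2 gives N = 97 for alpha 0.05, power 0.80, effect size 0.15 and six covariates. The noncentral F power for the overall regression test, with 6 and N − 7 degrees of freedom and noncentrality 0.15 × N, is 0.798 at N = 97, 0.804 at N = 98 and 0.813 at N = 100. The figure reproduces to within one dyad. It rests on baseline covariates only.

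**How many terms the rule could admit.** Section 5.2 lists six measures not marked baseline only: ADL, IADL, the 8-item memory scale, the recognition item, and proficiency for the care partner and for the PWMC. Baseline plus change for each gives 6 × 2 = 12 terms, against six budgeted. Twelve is a ceiling.

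**Set-up for the bias.** From the documents: 50 per arm; alpha 0.05, also taken as the entry threshold. Assumed, because the documents do not give them: SR's shift *a* in one covariate's change (in SD), the covariate-outcome slope *s*, and a true total benefit of 0.50 SD. Within-arm SDs are 1 and both variables are scored so that higher is better.

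- Covariate change: m = a·T + noise.
- Outcome change: y = (0.50 − s·a)·T + s·m + noise, so the total effect is always 0.50.
- The covariate enters only if its arm t-test gives p < 0.05.

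If the covariate always entered, the expected arm coefficient would be 0.50 − s·a; for a = 0.5 and s = 0.5 that is 0.25. Because it enters only sometimes, the mean under the rule lies between that value and 0.50.

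**Case 1: true benefit 0.50 SD.** Unadjusted power is about 70%. There were 20,000 simulated trials per scenario (4,000 for slopes 0.1 and 0.2). Cells give mean estimate in SD, then power.

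| Shift a | Covariate enters | s = 0.1 | s = 0.2 | s = 0.3 | s = 0.5 |
|---|---|---|---|---|---|
| 0.2 | 17% | 0.50, 68% | 0.48, 66% | 0.47, 66% | 0.46, 65% |
| 0.3 | 32% | 0.48, 66% | 0.47, 64% | 0.45, 60% | 0.42, 58% |
| 0.5 | 70% | 0.45, 60% | 0.42, 53% | 0.38, 46% | 0.29, 34% |
| 0.8 | 98% | not run | not run | 0.26, 24% | 0.10, 8% |

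With a = 0 there is no bias.

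**Case 2: no SR effect on the outcome.** The covariate and outcome correlate 0.3 to 0.5 within arm. If the covariate always entered, the bias would be minus correlation × a. Under the rule:

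| Shift a | Bias (SD) | Two-sided rejection |
|---|---|---|
| 0 | none | 4–5% |
| 0.2 | −0.02 to −0.04 | 5% |
| 0.3 | −0.05 to −0.08 | 6–7% |
| 0.5 | −0.13 to −0.21 | 10–22% |

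When the covariate moves in SR's favour, the excess rejections favour control: at a = 0.5, false benefit is 0.1–0.5% against a nominal 2.5%. If the covariate moves 0.5 SD against SR, the bias is +0.12 to +0.21 SD and false benefit is 9–21%.

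An independent repeat of both cases agreed to within about 0.01 SD and one percentage point.

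**The case against.** The strongest reply is that the damage depends on values nobody has. The plan gives no SR effect on any covariate and no slope. At a shift of 0.2 SD, or a slope of 0.1, the loss is modest. That is true, and the table shows it. It limits the expected size, but it does not make the rule sound: a valid efficacy model should not depend on the treatment leaving its covariates alone.

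A second reply is that few covariates are likely to move. ADL and IADL dependence are unlikely to respond to a reminder device, and recognition is only part of the 8-item scale. This is fair. The stronger candidates are device proficiency and the recognition content. Repeat measurement is explicit only for the 8-item scale. For proficiency it is implied by the heading covering all three surveys and by the rule's own reference to change scores.

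Third, the count of 12 terms needs every comparison to be significant. With no arm differences, about 12 × 0.05 = 0.6 would enter. The mismatch with section 17.2 is therefore an unbudgeted possibility, not a forecast.

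Fourth, the and/or wording permits baseline-only adjustment. It does, but it also leaves the choice of model open until the data have been seen.

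Finally, deaths, moves into long-term care and unblinded care-partner reporting can also produce arm differences in change. That is correct, and it gives no reason to adjust for them in this way.

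**Conclusion.** The concern holds and should be fixed before the efficacy analysis. As written, the rule lets post-randomisation variables into every Phase II efficacy model, selected by a test that picks those the treatment has most affected. Bias needs two conditions: SR shifts the covariate, and the covariate's change is related to the outcome. If either is absent there is none. Under the assumed ranges, harm is small for shifts near 0.2 SD and serious from about 0.5 SD. At 0.5 SD with slopes 0.3 to 0.5, a true 0.50 SD benefit is estimated at 0.38 to 0.29 SD and power falls from 70% to 46–34%. With a true null and correlations of 0.3 to 0.5, type I error reaches 10–22%. The direction depends on the sign of the shift.

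Selecting baseline covariates by significance test is a lesser fault: it makes the model data-dependent but does not by itself lose the randomised comparison.

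**What to change.** - **Sections 3.1 and 17.1:** remove change scores as covariates from the efficacy models. Name a short baseline-only set, within the six that section 17.2 allows, before any outcome is compared by arm, and use it whatever imbalance is observed. Baseline severity measured by the screening TICS-40 is one example.
- **Section 17.2:** make a matching edit, since it describes the six covariates as those that differ significantly between arms.
- **Change in proficiency and severity:** report arm differences as outcomes, or in a mediation analysis labelled exploratory.

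The cost is wording. The TICS-40 is already collected at screening, so no new data are needed, and the stated sample size already assumes baseline covariates only, so it does not change.

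### Section 17.2 takes its 97 dyads and 80% power from an overall six-predictor regression test, so power for the randomised-arm effect is not established

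*Combined protocol and SAP*

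**What the plan says.** **The planned test.** Sections 3.1 and 17.1 (Phase II Quantitative Analysis) plan a 2x2 repeated measures analysis of covariance on baseline and 6-month data. Section 17.1 states: "The primary independent variable in the proposed investigation consists of an indicator variable for random assignment into the SR treatment condition". It adds: "Outcomes will include statistical significance of within-subjects, or 6-month change, in those in the Smartwatch Reminder treatment or control groups on key outcome variables". Covariates enter only if they are found to differ significantly between arms.

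**The power statement.** Section 17.2 (Phase II) names repeated measures ANCOVA as the analysis and then says: "A sample size of 100 to identify a medium statistical effect (standardized regression coefficient = 0.15) at a suitable level of statistical power". It says this sample "is able to effectively incorporate up to 6 baseline covariates that vary significantly across the randomly assigned Smartwatch Reminder treatment and control conditions". The inputs are given as "an alpha level of .05, a medium effect size of .15 (as opposed to using specific measures", and the result is that "a multiple regression model (similar to an ANCOVA) that includes up to 6 covariates requires a sample size of 97". From this it concludes that "an expected sample size of 100 PWMC and care partner dyads will be sufficient to conduct the Phase II efficacy evaluation", and adds: "We anticipate having less than a 3% attrition rate which will ensure we maintain sufficient power".

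Neither section gives a between-arm difference, an SD, a baseline-to-6-month correlation or a covariate R-squared.

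**The concern.** The efficacy question is whether assignment to the smartwatch system changes outcomes. In a two-arm, two-visit design this is one degree of freedom: the arm effect on change from baseline to 6 months. The tabled figure appears to answer a different question, namely whether six predictors jointly explain any outcome variance. Section 17.2 calls those six predictors covariates, so the joint test could be significant with no effect of the intervention.

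The value 0.15 adds to the difficulty. The text names one metric for it, a standardized regression coefficient, and elsewhere calls it only a medium effect size. The named metric does not lead to 97 from the inputs given.

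Section 17.2 is the only quantitative support for the Phase II sample size. As it stands, a reader cannot tell what between-arm difference the trial was sized to detect, or whether the attrition allowance protects power for that difference.

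**Working it through.** **Inputs from the documents.** Alpha 0.05, power 0.80, the value 0.15, up to six covariates, a requirement of 97, 100 dyads planned and attrition under 3% (section 17.2); half of the dyads to each arm (section 5.2). Sidedness is not stated, so I assume two-sided tests, with alpha 0.05 per outcome.

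**Step 1: reproduce 97.** For an overall regression test with k predictors, power comes from the noncentral F distribution with k and N − k − 1 degrees of freedom and noncentrality λ = f² × N. Take f² = 0.15 and k = 6.

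- N = 97: λ = 0.15 × 97 = 14.55, degrees of freedom 6 and 90, critical F 2.20, power 0.798.
- N = 98: λ = 14.70, power 0.804.

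The smallest N for 80% is therefore 98, within one dyad of the stated 97. With five predictors it is 92. With seven (six covariates plus the arm) it is 103, and power is then 0.769 at 97 and 0.785 at 100.

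Other readings of 0.15 in the same six-predictor test do not return 97: as R-squared the N is 84, as Cohen's f it is 612, and as a standardized coefficient it is 599. That f-squared was meant is an inference from this match.

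**Step 2: the arm test, 0.15 as the standardized coefficient.** If covariates are uncorrelated with arm and explain a share R² of outcome variance, then f² = 0.15² / (1 − 0.15² − R²). The test has 1 and N − 8 degrees of freedom (arm plus six covariates).

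| Assumed covariate R² | f² | Power at 97 | Power at 100 | Dyads for 80% |
|---|---|---|---|---|
| 0 | 0.0225/0.9775 = 0.0230 | 0.32 | 0.32 | 343 |
| 0.50 | 0.0225/0.4775 = 0.0471 | 0.56 | 0.57 | 169 |
| 0.70 | 0.0225/0.2775 = 0.0811 | 0.79 | 0.80 | 99 |

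**Step 3: the arm test, 0.15 as the arm's partial f-squared.** With equal arms the difference is 2 × √0.15 = 0.77 residual SD. Power is 0.97 at both 97 and 100 dyads, and 55 dyads would give 80%.

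**Step 4: what 97 dyads can detect on the planned test.** I read the planned test as a between-arm comparison of change scores, with equal SDs at both visits and no covariates. The SD of a change score is √(2(1 − r)) single-visit SDs, where r is the baseline-to-6-month correlation. With 48.5 dyads per arm and 95 degrees of freedom, the noncentrality for 80% power is 2.830, so the detectable difference is

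2.830 × √(2/48.5) × √(2(1 − r)) = 0.575 × √(2(1 − r)).

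| Assumed r | √(2(1 − r)) | Detectable difference (single-visit SD) |
|---|---|---|
| 0.4 | 1.095 | 0.63 |
| 0.5 | 1.000 | 0.57 |
| 0.6 | 0.894 | 0.51 |
| 0.7 | 0.775 | 0.45 |

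Simulated power at these four differences, with 40,000 replicates each, was 0.804, 0.797, 0.800 and 0.797.

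**Step 5: effect of the covariate rule.** Covariates chosen because they differ by arm are correlated with arm. As an illustration, take six mutually uncorrelated covariates, each just at p = 0.05 (squared correlation with arm about 0.04) and unrelated to outcome. The variance of the arm estimate rises by 1/(1 − 6 × 0.04) = 1.32, and the detectable differences by √1.32 = 1.15, to 0.72 / 0.66 / 0.59 / 0.51 SD. Covariates that explain change would move them the other way.

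**The case against.** The strongest defence is that the arithmetic is sound. The table value reproduces, and 3% attrition from 100 does leave 97. Section 17.2 also partly discloses the substitution, since it names repeated measures ANCOVA as the analysis and describes the regression model only as similar. All of that stands. The problem is a mismatch between the calculation and the planned test, not a slip in the sums.

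Other limits also stand:

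- A reader might infer that a coefficient of 0.15 cannot be reconciled with 97 at all. It nearly can, if covariates explain about 70% of outcome variance (99 dyads; power 0.79 at 97). The plan states no such figure.
- A reader might see two conflicting named metrics. The text names one; the second use of 0.15 is unlabelled, and the conflict appears only on calculation.
- Group-by-time is the natural reading of a randomised 2x2 design, but sections 3.1 and 17.1 do not use the term, and one sentence in 17.1 can be read as change within each arm.
- Counting the arm as a seventh predictor matters little: 0.785 against 0.813 at 100 dyads.
- A null result would not be uninterpretable, because its confidence interval can be read without the planning calculation.

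**Conclusion.** The point holds as a mismatch that should be corrected. Section 17.2 does not establish 80% power for the arm effect. The 97 dyads belong to an overall six-predictor test under an inferred f-squared, and the one metric that the text names does not give 97 from the stated inputs. Depending on what 0.15 means, the one-degree-of-freedom arm test at 100 dyads has power from about 0.32 (coefficient, covariates explaining nothing) to 0.97 (partial f-squared, about 0.77 residual SD). The assurance about attrition fails for the same reason: it compares 100 with a number that is not an arm-effect requirement.

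A reader might infer that the trial is underpowered. The documents do not support that, because they give neither a target between-arm difference nor the correlation that the planned test depends on.

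These conclusions assume two-sided alpha 0.05 per outcome, equal arms and, for the change-score figures, equal SDs at both visits, no covariate adjustment and the listed values of r.

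**What to change.** Keep 100 dyads and the planned analysis. In section 17.2:

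- Delete the description of 0.15 as a standardized regression coefficient.
- Stop using 97 as the number required for the arm effect.
- Keep attrition under 3% as a stated assumption, without the claim that it secures power.
- Insert wording such as:

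> Assuming at least 97 of 100 dyads are evaluable at 6 months, two-sided alpha 0.05 per outcome, equal SDs at both visits and no covariate adjustment, the test of the between-arm difference in 6-month change has 80% power for 0.63 / 0.57 / 0.51 / 0.45 single-visit SD if the baseline-to-6-month correlation is 0.4 / 0.5 / 0.6 / 0.7 (assumed). Adjusting for covariates that are imbalanced between arms can increase these differences, and covariates that explain change can reduce them.

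If 0.15 was meant as f-squared for the arm, say so and give it as about 0.77 residual SD.

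The cost is a wording change in one section, with no effect on procedures, outcomes, analysis or recruitment. The downside is that the stated sensitivity becomes less favourable and rests on an assumed correlation.
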